- c Renal Flare (as defined in Section 8.1.6), Extrarenal SLE Flare (as defined in Section 8.1.7) may occur at any time during the study and Suboptimal Response (as defined in Section 8.1.8) after Week 26. Evaluation of Renal Flare requires a UPCR from a spot urine sample that is confirmed on a 24-hour urine collection, as well as 2 serum creatinine samples obtained within a 2-week period. Evaluation of Renal and Extrarenal SLE Flares or Suboptimal Response must be performed as soon as possible upon notification to the Investigator of symptom onset or lack of response. If Renal Flare or Extrarenal SLE Flare or Suboptimal Response occurs between scheduled visits, only the assessments for the Renal Flare/Extrarenal SLE Flare/Suboptimal Response Occurs on a scheduled visit, all scheduled assessments should be performed for that visit as well as any additional assessments required for the evaluation of the flare or lack of response.
- d Perform a symptom based neurologic examination if participant has complaints or clinical findings attributable to the CNS and if positive for findings, full neurologic examination to be performed at each assessment timepoint.
- In the LN cohort, placebo patients will receive only allowed concomitant therapy. For all other patients in both cohorts, see Figure 1 and Figure 2.

Note: If possible, all assessments should be performed prior to administration of study intervention on in-clinic dosing days, unless otherwise specified.

Abbreviations: CNS = central nervous system; D = day; ECG = electrocardiogram; ED = early discontinuation; IgAN = immunoglobulin A nephropathy; LN = lupus nephritis; NPTP = nonpharmacologic therapies and procedures; PE = physical examination; SLE = systemic lupus erythematosus; UPCR = urine protein to creatinine ratio; W = week; WOCBP = women of childbearing potential

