1.2. Schema

The study design schematic for the LN cohort is provided in Figure 1 and for the IgAN cohort in Figure 2.

Figure 1: Study Design Schematic (LN Cohort)

- ^a The optimal dose level will be identified based on the results of the Week 26 Primary Analysis for each cohort. Once identified, all participants on active treatment in that cohort who have at least 50 weeks of treatment will receive the selected optimal dose for the remainder of the study.
- b Participants will receive additional standard of care therapy in the event of a protocol-defined Renal Flare, or severe Extrarenal SLE Flare. Approved novel treatments for LN can be used per the Investigator's discretion. After Week 26, additional standard of care therapy for participants with Suboptimal Response is allowed at the clinical discretion of the Investigator in conversation with the Medical Monitor. However, if a CNI is used, ALXN2050 will need to be discontinued 3 days prior to CNI administration.
- ^c After completion of the Blinded Extended Treatment Period, participants in the placebo group will only receive allowed concomitant therapy during the Open-label Extension Period and will have the option to receive ALXN2050 180 mg bid or the optimal dose (if already identified) if the participant has a Renal Flare as defined in Section 8.1.6 or Suboptimal Response as defined in Section 8.1.8.

Abbreviations: bid = twice daily; CNI = calcineurin inhibitor; LN = lupus nephritis; SLE = systemic lupus erythematosus

Rlinded Initial Evaluation Blinded Extended Treatment Safety Screening Period Open-Label Extension Period Follow-up Period Period (up to 2 years/104 weeks) (up to 6 weeks) (26 weeks) (24 weeks) 30 days Optimal dose ALXN2050 + ALXN2050 180 mg bid + ALXN2050 180 mg bid + llowed concomitant therapy allowed concomitant therapy (N = 24)IgAN ALXN2050 120 mg bid + ALXN2050 120 mg bid + ALXN2050 + allowed concomitant therapy N = 56 Randomization 3:1:3 ALXN2050 + ALXN2050 180 mg bid + allowed concomitant therapy allowed concomitant therapy Placebo bid 4 (N = 12)allowed concomitant therapy ALXN2050 + ALXN2050 120 mg bid + (N = 24)lowed concomitant therapy allowed concomitant therapy (N = 12)Day 1 Week 26 Week 50 Week 154 Week 158 End of Treatment End of Study Primary Analysis Analysis 164 weeks

Figure 2: Study Design Schematic (IgAN Cohort)

Abbreviations: bid = twice daily; IgAN = immunoglobulin A nephropathy

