Physical examination, including neurological assessments ^f	х	X							Х		Section 8.2.1.	
Abbreviated PE			X	X	X	X	X	X				
Vital signs	X	X	X	X	X	X	X	X	X	X	Vital signs to be taken predose at clinic visits (Section 8.2.2).	
ECG for LN patients on hydroxychloroquine	Х	Х	Х	X	X	X	Х	Х	Х	X	Section 8.2.3.	
ECG for LN patients not on hydroxychloroquine	X	Х							X			
Prior medications and procedures	Х										Section 8.2.5.	
Concomitant medications and NPTP			Continuous monitoring							X	Section 6.5 and Section 8.2.5.	
Allowed concomitant LN therapy		Continuous monitoring								X	See details on corticosteroid taper in Section 6.5.3.1.	
Adverse events			Continuous monitoring								Section 10.3.	

Table 1: Schedule of Activities During Screening and the Blinded Initial Evaluation Period: Screening to Week 26 Visit (LN Cohort)

Period	Screen- ing			Initi	al Evalu	ation Pe		Notes			
Visit	1	2	3	4	5	6	7	8	9	Evaluation for Renal	Unscheduled visits can be performed
Week	Up to 6 W		W2	W4	W8	W12	W16	W20	W26/ ED ^b	Flare and Extrarenal	as needed. An ED Visit is required if participant discontinues study early.
Days and Window	D -42 to -1	D1	D15 ±3	D29 ± 3	D57 ± 5	D85 ± 5	D113 ±5	D141 ±5	D183 ± 5	SLE Flare Assessment Visit ²	
Predose blood sample for clinical chemistry, hematology, and coagulation	Х	X	X	X	X	X	X	X	X	x	Section 8.2.4.2 and Section 10.2.
Urinalysis and urine sediment	X	X	X	X	X	X	X	X	X	X	Section 8.2.4.3 and Section 10.2.
Participant safety card review		X	X	X	X	X	X	X	X	X	Confirm participants carry safety card at all times (Section 8.2.7).
PK and PD Assessments ⁸											
Predose blood sample for PK		X	X	X	X	X	X		X	X	
Predose blood sample for Bb and AP activity		X	X	X	X	х	X		X	x	See footnote for sampling timepoints.
Postdose blood sample for PK		X	X								
Postdose blood sample for Bb and AP activity		х	х								
Exploratory Assessments											
EQ-5D-5L		X			X		X		X		If possible, complete the PROs prior to
SF-36		X			X		X		X		procedures and intervention administration (Section 8.10).
FACIT-Fatigue		X			X		X		X		
SLEDAI-2K		X							X	x	Required at Day 1 and Week 26/ED; perform as needed for evaluation of Extrarenal SLE Flare (Section 8.1.7).
Blood and urine samples for biomarkers	Х	X	X		X		X		X	X	Collect predose on in-clinic dosing days (Section 10.2).

Table 1: Schedule of Activities During Screening and the Blinded Initial Evaluation Period: Screening to Week 26
Visit (LN Cohort)

Period	Screen- ing			Initi	ial Evalu	ation Pe	riod		Notes		

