Days and Window		D442 ± 14	D533 ± 14	D624 ± 14	D715 ±14	D806 ±14	D897 ±14	D988 ±14	D1079 ± 14	Extrarenal SLE Flare, and Suboptimal Response Assessment Visit (LN only) ^c	last dose	discontinues study early
General Assessments/Procedu	res											
Weight									X			
Pregnancy test (WOCBP only)		Х	Х	Х	X	Х	X	X	X		Х	Serum test required at ED; urine tests at all other visits (Section 8.2.6).
Efficacy Assessments												
24-hour urine collection					X				X	X		Obtain one 24-hour urine collection; Section 8.1.1
Morning spot urine sample		X	X	X	X	X	X	X	X	X		Section 8.1.2.
Monitor for Renal Flare and/or Extrarenal SLE Flare and/or Suboptimal Response (LN only)			Continuous monitoring							x		Refer to Section 8.1.6, Section 8.1.7, and Section 8.1.8 for definitions. Document use of additional standard of care therapy and/or repeat biopsy, if applicable (Section 6.5.4).
Blood samples for autoantibodies (LN only)										X		Section 10.2.

Table 5: Schedule of Activities During the Open-label Extension Period and Safety Follow-up Period (Both LN and IgAN Cohorts)

Period	Adhoc visit ^a		Open-label Extension Period								Safety Follow-up Period	Notes
Week	After W50	W63	W76	W89	W102	W115	W128	W141	W154/ ED ^b	Evaluation for Renal Flare.	4 weeks post last dose	Unscheduled visits can be performed as needed. An ED Visit is required if participant
Days and Window		D442 ± 14	D533 ±14	D624 ± 14	D715 ±14	D806 ±14	D897 ±14	D988 ±14	D1079 ±14	Extrarenal SLE Flare, and Suboptimal Response Assessment Visit (LN only) ^c	days post last dose	discontinues study early
Safety Assessments												
Physical examination, including neurological assessments ^d									X			Section 8.2.1.
Abbreviated PE		X	X	X	X	X	X	X			X	
ECG (only for LN patients receiving hydroxychloroquine)	X	X	X	X	X	X	X	X	X	X	X	Section 8.2.3
Vital signs		Х	Х	X	X	X	X	X	X	X	Х	Vital signs to be taken prior to dosing at clinic visits (Section 8.2.2).
Concomitant medications and NPTP				(Continuou	s monitori	ng			X	X	Section 6.5 and Section 8.2.5.
Allowed concomitant LN or IgAN therapy			Continuous monitoring							X	X	Section 6.5.3.1 and Section 6.5.3.2.
Adverse events			Continuous monitoring							X	X	Section 10.3.
Blood sample for clinical chemistry, hematology, and coagulation		Х	Х	Х	X	X	X	X	X	X		Section 8.2.4.2 and Section 10.2.

Table 5: Schedule of Activities During the Open-label Extension Period and Safety Follow-up Period (Both LN and IgAN Cohorts)

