Period	Adhoc visit ^a		Open-label Extension Period							Safety Follow-up Period	Notes	
Week	After W50	W63	W76	W89	W102	W115	W128	W141	W154/ EDb	Evaluation for Renal Flare,	4 weeks post last dose	Unscheduled visits can be performed as needed. An ED Visit is required if participant
Days and Window		D442 ± 14	D533 ± 14	D624 ± 14	D715 ±14	D806 ±14	D897 ± 14	D988 ±14	D1079 ±14	Extrarenal SLE Flare, and Suboptimal Response Assessment Visit (LN only) ^c	30 (± 3) days post last dose	discontinues study early
Urinalysis and urine sediment		X	X	X	X	X	X	X	X	X		Section 8.2.4.3 and Section 10.2.
Participant safety card review		X	X	X	X	X	X	X	X	X		Confirm participants carry safety card at all times (Section 8.2.7).
Study Intervention•												
Study intervention compliance and accountability		Х	Х	Х	X	Х	Х	X	X			Participants on study intervention should bring all unused study intervention at each clinic visit for tablet counting.
Study intervention dispensing	c IN	х	х	х	х	X	х	х		120 11		Participants on study intervention will be provided with sufficient study intervention to last until their next study visit (except at W154 and ED).

^a Adhoc visit is only applicable for LN patients who are receiving hydroxychloroquine: When patients are switched from 120 mg to 180 mg after Week 50, or when placebo patients who are on allowed concomitant therapy initiate ALXN2050 at any dose due to a Renal Flare, additional ECG needs to be obtained at an adhoc visit 2 weeks (± 7 days) after the dose initiation or dose escalation.

^b For participants who discontinue study intervention prior to the end of the Open-label Extension Period, the ED Visit should be performed as soon as possible and a Safety Follow-up Visit should be performed 30 days after the last dose of study intervention.

Table 5: Schedule of Activities During the Open-label Extension Period and Safety Follow-up Period (Both LN and IgAN Cohorts)

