4.1.4. Open-label Extension Period

After completion of all assessments at the end of the Blinded Extended Treatment Period (Week 50 Visit), all participants will have the opportunity to enter an OLE Period and receive ALXN2050 for up to 2 years (104 weeks) if no relevant side effects (in the opinion of the Investigator) and no Treatment Failure (LN cohort) are present. During the OLE Period:

- Participants in the LN cohort randomized to the active treatment groups will continue to receive the same dosing regimen as assigned during the Blinded Extended Treatment Period.
- Participants in the LN cohort randomized to the placebo group will no longer receive
 placebo and will continue to receive allowed concomitant therapy alone. These
 participants will have the option to receive ALXN2050 180 mg bid or the optimal
 dose (if already identified) if the participant has a Renal Flare as defined in
 Section 8.1.6 or Suboptimal Response as defined in Section 8.1.8.
- Participants in the IgAN cohort will continue to receive the same dosing regimen as assigned during the Blinded Extended Treatment Period.
- Participants in both cohorts receiving ALXN2050 who complete at least 50 weeks of treatment will receive the optimal dose level of ALXN2050 (180 mg or 120 mg bid) once an optimal dose is identified based on results of the primary analysis at Week 26 and/or Data Monitoring Committee (DMC) review of the safety and efficacy data.
- Percentage change in proteinuria from baseline and change from baseline in eGFR at Weeks 102 and Week 154 will be assessed as exploratory efficacy endpoints. Safety and tolerability will also be evaluated continually throughout the OLE Period.

After completion of the study or after ED, a Safety Follow-up Visit will be conducted 30 days after the last dose of study intervention.

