8.1.1.1. LN Cohort

For participants in the LN cohort, proteinuria will be measured by UPCR. A single 24-hour urine collection will be obtained at Screening to assess eligibility. Two separate 24-hour urine collections will be obtained within 2 weeks prior to the Week 26 Visit (to assess the primary endpoint) and Week 50 Visit (to assess a secondary endpoint). Additional 24-hour urine collection is also scheduled for Week 102 and Week 154.

Confirmation of a protocol-defined Renal Flare or Suboptimal Response requires a single 24-hour urine collection within 2 weeks of the spot urine sample (Section 8.1.6 and Section 8.1.8).

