8.2.3. Electrocardiograms

- Single 12-lead electrocardiograms (ECGs) will be conducted locally as outlined in the SoA (Section 1.3) to obtain heart rate, PR interval (time from the onset of the P wave to the start of the QRS complex), combination of the Q wave, R wave, and S wave (QRS) interval, QT, and the QTc interval(s). QT interval will be corrected for heart rate using Fridericia's formula.
- Participants must be supine for approximately 5 to 10 minutes before ECG collection and remain supine but awake during ECG collection.
- The Investigator will be responsible for reviewing the ECG to assess whether the ECG is within normal limits and determine the clinical significance of the results.
- Results will be recorded on the eCRF. Clinically significant findings should be recorded on the AE form.

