26-week Blinded Initial Evaluation Period. The LN cohort will continue with the same treatment allocation during the 24-week Blinded Extended Treatment Period (ALXN2050 180 mg bid, ALXN2050 120 mg bid, or placebo bid). For the IgAN cohort, participants assigned to the placebo group will also be assigned to their active study treatment for the 24-week Blinded Extended Treatment Period (ALXN2050 120 mg bid or ALXN2050 180 mg bid) in a 1:1 allocation ratio at the time of initial randomization.

The randomization stratum is defined as follows:

[figure not shown]
- LN cohort: corticosteroid induction treatment initiation (prior to Screening, during Screening Period)
- IgAN cohort: mean proteinuria from 2 valid 24-hour urine collections (1 to 2 g/day, > 2 g/day)

During the OLE Period, participants in both cohorts receiving ALXN2050 during the 24-week Blinded Extended Treatment Period will continue their active treatment at the same dose level. Once an optimal dose is identified based on results of the primary analysis at Week 26 for each cohort and/or Data Monitoring Committee review of the safety and efficacy data, all participants in that cohort with at least 50 weeks of study treatment will receive the optimal dose of ALXN2050. Participants in the LN cohort randomized to the placebo group will no longer receive placebo and will continue to receive allowed concomitant therapy alone. These participants will have the option to receive ALXN2050 180 mg bid or the optimal dose (if already identified) if the participant has a renal flare or suboptimal response.

In the LN cohort, participants who meet the criteria for protocol-defined renal flare or for extrarenal systemic lupus erythematosus (SLE) flare will receive additional standard of care therapy. After Week 26, participants may also receive additional standard of care therapy for protocol-defined suboptimal response. The specific choice of additional standard of care therapy(ies) is generally at the discretion of the Investigator.

Participants who discontinue study intervention and remain on study may receive treatment consistent with local standard practice for their disease per Investigator judgment.

[figure not shown]
Figure 1: Study Design Schematic (LN Cohort)

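### The 2-week ECG after a late ALXN2050 start in LN placebo participants on hydroxychloroquine is tied to Renal Flare only, so those starting for Suboptimal Response miss it

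*Protocol*

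**What the plan says.** **Who may start ALXN2050 after Week 50.** Figure 1 footnote c gives LN placebo participants the option "if the participant has a Renal Flare as defined in Section 8.1.6 or Suboptimal Response as defined in Section 8.1.8". The synopsis and Protocol Section 4.1.4 offer the same two routes. SAP Section 1.2 agrees, describing the "option to receive ALXN2050 180 mg bid or the optimal dose (if already identified) if the participant has a renal flare or suboptimal response".

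**Who gets the early ECG.** Table 5 footnote a restricts the ad hoc visit to LN participants on hydroxychloroquine and names two triggers. One is a switch from 120 mg to 180 mg after Week 50. The other is when placebo participants "initiate ALXN2050 at any dose due to a Renal Flare, additional ECG needs to be obtained at an adhoc visit 2 weeks" later, give or take 7 days. Suboptimal Response is not mentioned.

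**What else governs ECGs.** Section 8.2.3 adds no timing of its own and defers to the Schedule of Activities. In Table 5, hydroxychloroquine users have an ECG at every scheduled extension visit, at the flare or Suboptimal Response assessment visit, and at Safety Follow-up. In the blinded period, the Table 1 row "ECG for LN patients on hydroxychloroquine" is marked at every visit, including Week 2 (Day 15 ± 3). Section 7.1 withdraws hydroxychloroquine users for a QT/QTc above 500 msec, or a rise of more than 60 msec from baseline, confirmed on recheck.

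**The concern.** The ECG trigger is narrower than the permission to start the drug. The plan bars drugs that significantly prolong QTc but exempts hydroxychloroquine in LN (exclusion criterion 8, Section 6.5.2), and Section 6.5.1 strongly recommends antimalarials such as hydroxychloroquine. It balances that exemption with extra ECGs and the Section 7.1 withdrawal rule. Section 4.3 reports more than dose-proportional exposure at steady state and large variability between subjects, so a check about two weeks into dosing makes sense.

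Why a participant starts ALXN2050 changes neither the drug nor the hydroxychloroquine exposure, yet the first on-drug check comes later for one permitted reason than for the other. The documents give no ground for the difference. The Section 7.1 rule cannot act on an ECG that has not been taken, so for these participants it takes effect later.

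**Working it through.** The plan gives no figure to reproduce. The check compares the text across sections and then applies the visit days.

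**1. ALXN2050 starts and escalations in LN hydroxychloroquine users**

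| Event | ECG required about 2 weeks later? | Source |
|---|---|---|
| First blinded dose, Day 1 | Yes, Week 2 (Day 15 ± 3) | Table 1 |
| Switch from 120 mg to 180 mg after Week 50 | Yes, 2 weeks ± 7 days | Table 5 footnote a |
| Placebo to ALXN2050 for Renal Flare | Yes, 2 weeks ± 7 days | Table 5 footnote a |
| Placebo to ALXN2050 for Suboptimal Response | No | No section requires it |

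The assessment-visit ECG does not fill the gap. That visit serves to establish that the participant qualifies, so it comes before the first dose.

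**2. Time to the first required on-drug ECG**

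Inputs are the Week 50 visit at Day 351 ± 7 (Table 3) and the extension visits at Days 442, 533, 624, 715, 806, 897, 988 and 1079, each ± 14 (Table 5).

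- Spacing: 442 − 351 = 91 and 533 − 442 = 91; every later pair to Day 1079 also gives 91 days.
- Renal Flare route: 14 ± 7 = 7 to 21 days.
- Suboptimal Response route, start at a scheduled extension visit: nominally 91 days. With both ± 14 windows, 91 − 28 = 63 to 91 + 28 = 119 days.
- Start at the Week 50 visit: nominally 91 days. With windows of ± 7 and ± 14, 91 − 21 = 70 to 91 + 21 = 112 days.
- Start 14 days after a scheduled visit: 91 − 14 = 77 days. The 14 days come from Section 8.1.1.1: "Confirmation of a protocol-defined Renal Flare or Suboptimal Response requires a single 24-hour urine collection within 2 weeks of the spot urine sample". That limit concerns the urine collection, not the first dose, so a start later than this waits less than 77 days.

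**3. Illustrative average**

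Assume start days are spread evenly over the 91-day interval; the documents neither support nor contradict this.

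- Mean wait: 91 / 2 = 45.5 days.
- Share with no required on-drug ECG by day 21: (91 − 21) / 91 = 70 / 91 = 77%.

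**4. Number affected**

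The ceiling is the approximately 30 LN placebo participants in Table 8. Nothing narrower can be computed, because the documents give neither hydroxychloroquine uptake nor a rate of ALXN2050 starts after Week 50.

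**The case against.** The strongest reply is that little is lost. Hydroxychloroquine users keep the pre-start ECG and every scheduled extension ECG. Unscheduled visits are allowed, and each Suboptimal Response must be discussed with the Medical Monitor. Other significantly QTc-prolonging drugs are prohibited. Table 6 does not list QT prolongation among the risks, and no section quantifies a QT effect of ALXN2050, alone or with hydroxychloroquine. All of this is true, and it keeps the point modest: harm from a later first ECG cannot be shown from these documents. But unscheduled visits are discretionary, whereas the sponsor made this ECG mandatory on the parallel route.

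A second reply is that the route is narrow. Section 4.1.4 makes absence of Treatment Failure a condition of the extension, and Section 8.1.8 counts Suboptimal Response as Treatment Failure. Some later cases would also meet the Renal Flare definition and so trigger the ECG. This may reduce the numbers but does not close the route. The synopsis carries no such condition, Section 8.1.9 defines Treatment Failure by receipt of additional therapy, and Section 4.1.4 itself still offers ALXN2050 for Suboptimal Response.

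Third, 91 days is a worst nominal case. Routine 24-hour urine in the extension is scheduled only at Weeks 102 and 154, so detection, confirmation and start at one visit would be unusual. That is fair. On the other hand, Table 5 marks dispensing only at scheduled visits, so a start deferred to the next visit is possible. The same facts weaken the even-spread assumption, and the 45.5-day and 77% figures should be read as illustration only.

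**Conclusion.** The gap is real. Footnote a omits one of the two permitted reasons for starting ALXN2050, and no other section supplies the missing ECG. In LN hydroxychloroquine users, Suboptimal Response starters are the only group beginning or escalating ALXN2050 without a required ECG at about two weeks.

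The consequence is a delay in the first required on-drug ECG, from 7 to 21 days to as much as 91 days on nominal visit days, or 119 at the window extremes. Those figures rest only on the tabulated visit days. The Section 7.1 rule is postponed, not disabled. The number affected is unknown and probably small, since ALXN2050 is only an option on this route. The point concerns the safety schedule and does not touch the primary or Week 50 efficacy analyses. It should be fixed because the inconsistency is plain and the correction costs almost nothing.

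**What to change.** In Table 5 footnote a, either delete the Renal Flare condition on placebo participants' starts or add Suboptimal Response beside it. The ad hoc ECG would then follow any ALXN2050 start in LN placebo participants on hydroxychloroquine, with the first required on-drug ECG at 7 to 21 days on both routes. The ad hoc column and the 2-week (± 7 days) window stay as they are.

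The cost is one phrase in the next protocol amendment and one ECG per affected participant at a visit type that already exists. SAP Section 1 records that study intervention has been paused since 06 Sep 2024, so the change should be in place before dosing resumes, if it does.
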